4.4 Safety Endpoints

Safety outcomes include:

- Solicited AEs through 7 days post vaccination (based on the review of diary card data),
- Unsolicited AEs through 28 days post vaccination,
- SAEs through 6 month post vaccination,
- AEs of special interest through 6 month post vaccination
- Serious adverse drug reactions (ADRs) through the entire study duration
- Laboratory safety tests
- Pregnancy outcomes
- SARS-CoV-2 serostatus

5 STUDY POPULATIONS

5.1 Analysis Populations

Sponsor authorization of the assigned analysis populations is required for the primary analysis, the secondary analysis (after all participants have at least 36 months of follow-up/have discontinued early), and for the final analysis. Agreement and authorization of participants included/excluded from the Per Protocol (PP) population for the primary analysis will be obtained prior to any unblinding activities. Reason(s) for exclusion from the PP population will be applied consistently across all participants with detailed documentation.

	Description
Enrolled population	All participants who provide informed consent.
Randomized population	All participants randomly assigned to study intervention. A participant will be programmatically included in this analysis population if the participant has a randomization number and date of randomization. Participants will be analyzed according to the intervention they were randomized to.
Modified intention to treat (mITT) efficacy population	All participants randomly assigned to study intervention who received the study intervention, and are QFT negative at the Day 71 visit, or at the first study visit post Day 71 for which a QFT result is available if the Day 71 study visit was missed or the Day 71 QFT result was not available [1]. Participants will be analyzed according to the intervention they were randomized to.
Per Protocol (PP) efficacy population	All participants in the mITT population who did not substantially deviate from the protocol procedures and who received the treatment to which they were randomized. Participants who substantially deviated will be identified prior to database lock and unblinding [2]. Participants will be analyzed according to the intervention they were randomized to.
Safety	All participants randomly assigned to study intervention who received the study intervention. Participants will be analyzed according to the intervention they received.

[1] Because of COVID-19, many study participants enrolled less than 70 days prior to the enrollment pause on 19 March 2020, may have missed their Day 71 visit. Participants who missed Day 71 visit are eligible for inclusion in the mITT population if their first QFT result post randomization is negative and are excluded from the mITT population if their first QFT result post randomization is not negative.

[2] Protocol deviations will be evaluated individually by the sponsor to decide whether it has basis to exclude a participant from the PP population.

5.2 Subgroups

The consistency of results with respect to the primary and secondary objectives will be examined within the following subgroups using the mITT analysis population:

- Study site / school quintile (refer to Appendix 3)
- Sex (Male, Female)
- Age Group (10-11 years, 12-14 years, >14 years)
- Method of reporting previous BCG vaccine (scar, self-reporting, or written documentation)

6 CHANGES IN CONDUCT OR PLANNED ANALYSES FROM THE PROTOCOL

ITT efficacy analysis population was mentioned in the Protocol and has been removed from the SAP as no specific analyses are planned based on the ITT population.

7 OVERALL STATISTICAL CONSIDERATIONS

7.1 Research Hypotheses

Primary: Revaccination with BCG reduces the risk of sustained *Mtb* infection (defined for this protocol as sustained QFT conversion) versus placebo in previously BCG vaccinated, QFT negative healthy adolescents.

Secondary (hierarchical):

- Revaccination with BCG reduces the risk of sustained *Mtb* infection versus placebo in previously BCG vaccinated, QFT negative healthy adolescents, with vaccine efficacy (VE) durability that lasts at least 36 months.
- Revaccination with BCG reduces the risk of sustained *Mtb* infection versus placebo in previously BCG vaccinated, QFT negative healthy adolescents, with VE durability that lasts at least 48 months.

7.2 Determination of Sample Size

The primary analysis will be triggered after the number of required events to achieve 90% power with a 1-sided alpha of 2.5% has been accrued. If the true vaccine efficacy is 45%, at least 118 events are required to achieve 90% power or greater.

The proposed sample size was determined based on targeting a relatively high probability (~80%) of obtaining the required 118 sustained conversion events within 3.5 years of the study start. The probability of obtaining the required 118 sustained conversion events within 3 and 3.5 years of study start are shown in Table 2 for sample sizes ranging from 600 to 800 in the mITT efficacy population, under the assumptions described herein. Due to COVID-19 related restrictions, it will likely take longer to complete enrollment and to reach the number of events needed for the primary analysis.

After accounting for the expected 7% participants to be ineligible for the mITT efficacy population due to a positive QFT assay result at Day 71, the table shows that randomizing approximately 800 participants to each treatment group is sufficient to detect a true VE of at least 45% under the specified assumptions, resulting in ~80% probability to accrue the required number of events (118) within 3.5 years of study initiation when the attack rate is as low as 8%. Since it is expected that approximately 12% of the population enrolled will be 10- or 11-year-old adolescents, where there is limited information on the attack rate and potential VE, a further inflation of the required 800 participants per group by 12% resulted in a final proposed sample size of 900 participants per group, or a total of 1800 participants. Approximately 6720 participants will be screened to enroll and randomize up to 2150 participants.

Table 2: Sample Size Requirements to Ensure 75%-80% Probability of Performing the
Primary Analysis within 3.5 years

	Attack ra	te = 10%	Attack rate = 8%				
N/group	Prob	Prob	Prob	Prob			
mTTT	(analysis	(analysis	(analysis	(analysis			
Efficacy	$in \leq 3$	in ≤3.5	$in \le 3$	in ≤3.5	N/group	N/group	Final N
Population	yrs)	yrs)	yrs)	yrs)	Randomized*	(+12%)**	(Total)
600	4.3	75.4	< 0.1	5.4	646	723	1446
650	21.9	94.0	0.2	20.8	699	783	1566
700	50.4	99.4	0.8	52.7	753	844	1688
750	77.0	>99.9	5.3	80.2	807	904	1808
800	93.0	>99.9	20.5	94.5	861	964	1928

Assumes equal randomization (randomization ratio 1:1)

Probability analysis occurs within 3 and 3.5 years (yrs) based on 2000 simulations, assuming 1 yr accrual, 70% of primary infection remain sustained, 5% annual drop-out rate

- *Assumes 7% removed from those randomized due to QFT + result at Day 71
- ** Assume additional 12% of participants will be 10 or 11 year olds, where we have limited information on attack rate and potential VE

7.3 General Conventions

Frequency (n) and percentages (%) will be used to summarize categorical variables; mean, standard deviation (SD), median, minimum, and maximum will be used to summarize continuous variables.

Decimal precision for summary statistics of continuous variables will be based on the mean value. Typically, the mean will contain one more decimal place than actual values but the decimal precision may vary in order to obtain an organized and understandable table or listing. The median will contain the same number of decimal places as the mean; the standard deviation will contain one more decimal place than the mean; and the minimum and maximum will contain one less decimal place than the mean.

Unless otherwise specified, the denominators for percentages will be the number of participants in each treatment group with non-missing data for the variable of interest.

The day of receiving study intervention is defined as Study Day 1 or Day 1. All other study days will be computed relative to Day 1.

- For events on or after Day 1, study day for a particular event or visit will be calculated as Date_{event} Date_{Day 1} + 1.
- For events before Day 1, study day for a particular event will be calculated as Date_{event}-Date_{Day 1}. Day 0 will not be used.

All data will be presented by treatment group.

For a given parameter (e.g. y) change from baseline (CFB) will be calculated as $y_t - y_b$ where y_t is a given participant's value t days post-baseline and y_b is a given participant's value at baseline. CFB will be computed for participants with both a baseline value and a post-baseline value. If a participant is missing a post-baseline value, there will be no imputation of the missing value. Only observed case data will be used for post-baseline analyses. For parameters which are not fully numeric, CFB will not be computed and values will be summarized in a listing.

7.4 **Baseline Definition**

Unless otherwise specified, baseline is defined as the last non-missing assessment (scheduled or unscheduled) prior to the study vaccination. In the case where the last non-missing assessment and the reference start date coincide, that assessment will be considered pre-vaccination (baseline). For example, if laboratory assessments fall on the date of study vaccination and the time of the assessment is missing, the applicable assessment will be considered as baseline. However, adverse events starting on the reference start date (date of study vaccination) will be considered as treatment-emergent, therefore post-baseline.

7.5 Handling of Missing Data

Missing data will not be imputed. Handling rules of indeterminate or missing QFT results are included in Section 9.1.

7.6 **Pooling Strategy for Study Sites**

This study is being conducted at multiple sites in various regions within South Africa. One site, Site 103, will enroll participants from various schools in the region.

Generally, all schools/regions will be pooled by intervention for analysis purposes. Because it is expected that enrollment at some sites or schools by socio-economic status quintiles might be low, the analysis of the primary efficacy will not include study site or school in the model. Efficacy analyses will be presented by subgroup = site/school quintile. Details are provided in the relevant SAP sections.

7.7 Visit Windows/Unscheduled Visits

Visit windows will not be applied for the purposes of identifying sustained conversion.

Primary and secondary efficacy endpoints analysis based on the mITT and PP efficacy populations will use the visits designation (e.g., Day 84 post conversion) as the visit date in the study database, regardless of when the actual visit took place within the protocol-specified window (i.e., including out-of-window visits).

Missed visits due to COVID-19 related restriction with telephone contact performed will be documented as protocol deviations.

For participants who converted (QFT negative to QFT positive), the 1-month post initial QFT conversion visit (labeled as Post QFT Conversion Day 28 on the eCRF) will be relabeled to Month (x + 1 month),

where x is the visit where the participant originally converted to QFT positive, for display purposes of the relevant assessments (i.e., focused physical examination, TB symptom screen). For example, if the participant converted to QFT positive at Month 3, then the Post QFT Conversion Day 28 visit will be relabeled to Month (3 + 1), therefore Month 4.

Similarly, the 3-month post initial QFT conversion visit (labeled as Post QFT Conversion Day 84 on the eCRF) will be relabeled to Month (x + 3 months) for display purposes of the relevant assessments (i.e., focused physical examination, TB symptom screen, and QFT assay).

Unscheduled visits will not be included in by-visit summaries or analyses but may contribute to the baseline value and worst post-baseline assessments. In the case of a retest (i.e., when the same visit number is assigned), the latest available test result as provided in the data transfer for that visit/time point will be used for by-visit summaries. Unscheduled QFT assessments may contribute to the determination of initial and sustained conversions.

7.8 Multiplicity

The primary analysis will be triggered when at least N=118 sustained *Mtb* infection events (defined as QFT conversion from a negative to positive test result, as per QuantiFERON-TB Gold Plus Package Insert) in the mITT efficacy population have accrued.

The primary efficacy endpoint (Section 4.3.1) will be analyzed using a log-rank test, stratified by sex and age group (10-11 years old, 12-14 years old, and >14 years old) to evaluate differences in the distributions of event times between the BCG vaccination and placebo groups. The two durability analyses will be performed: the first one after all participants in the mITT efficacy population have either prematurely discontinued the study or have at least 36 months of follow-up (secondary analysis; a data cutoff date will be established at the date of each participants Month 36 visit) and the second one after all participants in the mITT efficacy population have completed 48 months of follow-up at the end of study (final analysis).

Therefore, the following null hypotheses: $H_{01} \rightarrow H_{02} \rightarrow H_{03}$ will be assumed:

- H_{01} corresponding to the primary analysis (at least N=118 sustained QFT conversion events in the mITT efficacy population have accrued): $S_{s,BCG}(t) = S_{s,Pbo}(t)$
- H_{02} corresponding to the secondary analysis (when all participants have prematurely discontinued the study or have at least 36 months of follow-up): $S_{s,BCG}(t) = S_{s,Pbo}(t)$
- H₀₃ corresponding to the final analysis (when all participants have prematurely discontinued the study or have completed the study with 48 months of follow-up): S_{s,BCG}(t) = S_{s,Pbo}(t)

for strata s=1, 2, ..., 6 (6 strata = sex and age group [10-11 years old, 12-14 years old, and >14 years old]), where S(t) is the survival probability (probability that a participant's time to sustained *Mtb* infection > t).

To account for multiple testing, a step-down approach will be used to preserve the overall Type I error at a one-sided 2.5%. Specifically, if the one-sided p-value associated with the primary hypothesis H_{01} of BCG vaccine efficacy relative to placebo (p_1) is less than or equal to 0.025, the durability of the vaccine efficacy after all participants have 36 months of follow-up (H_{02}) will be formally assessed. If both H_{01} and H_{02} are rejected at one-sided 2.5% then the H_{03} will be formally assessed at one-sided 2.5%.

Once a hypothesis is not rejected, no further testing is formally permitted.

Any inferential statistics calculated for the exploratory objectives/endpoints are for exploratory/descriptive purposes only.

8 STATISTICAL ANALYSIS METHODS

A database freeze and unblinding is planned for the primary analysis (Section 4.2.2) after at least 118 sustained *Mtb* infections (defined as QFT conversion from a negative to positive test result, as per QuantiFERON-TB Gold Plus Package Insert) occur in the mITT efficacy population. An additional follow-up database freeze is planned for the secondary analysis (Section 4.2.3) after all participants have completed 36-months of follow-up or prematurely discontinued the study. A full database lock and final analysis (Section 4.2.4) is planned after all participants have completed 48 months of follow-up or prematurely discontinued the study.

Planned analyses for reporting disposition, protocol deviations, demographics, baseline characteristics, and treatment exposure are included in this section (Section 8).

Planned analyses for efficacy parameters are included in Section 9. Analysis of safety and tolerability can be found in Section 10. Other relevant data analyses/summaries are described in Section 11.

8.1 Disposition

All participants who provide informed consent will be accounted for in this study.

The number of participants screened, re-screened, number of screening failures, screening failure participants who were QFT positive at Screening, and the number of participants randomized will be summarized for all screened participants per site and overall.

Participant disposition and withdrawals (including reasons for discontinuation as provided on the electronic case report form [eCRF]) will be summarized and listed for the randomized analysis population.

A summary table containing the number of participants in each analysis population and reasons for exclusion from each analysis population will be provided.

8.2 **Protocol Deviations**

Protocol deviations (PDs) for this study will be documented in IBM-CD (the online study database). Although IQVIA's clinical trial management system (CTMS) was used until July 2020, IBM-CD was updated during July 2020 to include unique identifiers and to accommodate participant and site level protocol deviations. Following the data migration, the IQVIA team moved PDs documented in IQVIA CTMS to IBM-CD.

Protocol deviations will be summarized for the randomized analysis population by major deviation categories and will be included in a by-participant data listing.

Sites and all relevant parties involved were instructed to track all protocol deviations related to COVID-19 proactively. Protocol deviations due to the COVID-19 pandemic will be described in the clinical study report based on study records.

A separate by participant listing will be generated for protocol deviations related to COVID-19.

8.3 Demographics and Baseline Characteristics

Demographic data and other baseline characteristics will be summarized using descriptive statistics for the Safety population, mITT efficacy population, and the PP efficacy population.

The denominators for percentages will be the number of participants in each treatment group with non-missing data available for the variable of interest.

The following characteristics will be summarized:

- Age (years) and Age group (10-11 years, 12-14 years, >14 years)
- Sex (Male, female)
- Race (Asian, Asian Indian, Black, South African Coloured, White, Other, Mixed Race)
- Ethnicity (Hispanic or Latino, Not Hispanic or Latino, Not Reported, Unknown)
- Weight (kg)
- Height (cm)
- Body mass index (BMI) (kg/m²)

BMI (kg/m^2) will be calculated using the following formula:

$$BMI = \frac{weight (kg)}{height (m) \times height (m)}$$

• Method of reporting previous BCG vaccine (scar, self-reporting, or written documentation)

Additionally, a by-participant listing will report the above listed characteristics, as well as study site / school quintile (refer to Appendix 3).

8.4 Treatment Exposure and Compliance

Participants will be administered a single dose of BCG vaccine or placebo.

The date and time of the vaccine administration will be listed for each participant. Treatment compliance is not relevant and will not be calculated. Diary completion/compliance will be calculated as described in the respective Section 10.4.

9 EFFICACY ANALYSES

9.1 **Primary Analysis**

The primary efficacy endpoint will be analyzed when at least N=118 sustained *Mtb* infection events (defined as QFT conversion from a negative to positive test result, as per QuantiFERON-TB Gold Plus Package Insert) in the mITT population have accrued.

The primary efficacy endpoint (sustained QFT conversion as defined in Section 4.3.1) will be analyzed using a log-rank test, stratified by sex and age group (10-11 years old, 12-14 years old, and >14 years old) to evaluate differences in the distributions of event times between the BCG vaccination and placebo groups.

Censoring and event times will be defined as follows:

- For participants with sustained QFT conversion (censor = 0), time to event will be derived in days as (date of initial conversion date of Day 71 +1) and converted to months. Note that Day 71 here refers to either Day 71 or, if missed, the first in-person visit after Day 71. Date of initial conversion = date of a positive QFT test observed after a negative result at Day 71 or after a negative test at the first in-person visit after Day 71 if the Day 71 visit was missed.
- For participants without sustained QFT conversion (censor = 1), censoring time will be derived in days as (censoring date date of Day 71 + 1) and converted to months. Again, Day 71 refers to either Day 71 or, if missed, the first in-person visit after Day 71.

The censoring date for participants without sustained QFT conversion is the last date at which a non-missing QFT result is available prior to the date of data cut-off. There are several scenarios in which participants may have an initial QFT conversion but fail to meet the requirements for sustained QFT conversion due to subsequent negative, missing, or indeterminate QFT results. Appendix 6 provides details on derivation of event and censoring times for all the expected possible scenarios.

Conventions for additional scenarios not covered in Appendix 6, but based on actual data may need to be considered and detailed in the ADaM specifications prior to all planned analyses. An indeterminate test result will be interpreted as negative for the derivation of a participant's time to event.

For the sustained conversion analysis based on the PP efficacy population, which is a subset of the mITT efficacy population, sustained QFT conversion including events and censoring and event times will be defined the same way as for the analysis based on the mITT efficacy population. The sustained conversion analysis based on the PP efficacy population will be performed both with and without stratification factors.

The null and alternative hypothesis in terms of the survival functions S(t) and the 6 strata: sex and age group (10-11 years old, 12-14 years old, and > 14 years old) are (Klein & Moeschberger [1997]):

H₀: $S_{s,BCG}(t) = S_{s,Pbo}(t)$, for all strata s=1, 2, ..., 6 versus

H₁: $S_{s,BCG}(t) > S_{s,Pbo}(t)$, in some stratum s=1, 2, ..., 6.

The primary null hypothesis will be rejected if the 1-sided p-value associated with evaluating whether the event-free distribution is longer in the BCG vaccination group relative to the placebo group is less than or equal to 0.025. SAS PROC LIFETEST will be used for this analysis (Appendix 7).

Summaries of the number and percentage of participants experiencing a sustained QFT conversion and participants censored (overall and by reason for censoring including participants who discontinue and are censored at date of discontinuation) will be provided along with median (and 95% confidence interval [CI]) time of sustained QFT conversion (displayed in months) for each treatment group.

The hazard ratio (HR) and 95% CIs will be estimated from a stratified Cox Proportional Hazards model with sex and age group (10-11 years old, 12-14 years old, and > 14 years old) as stratification variables. The primary results will be based on stratification as per interactive voice response system (IVRS).

To assess the robustness of the primary results due to the change in randomized strata, a sensitivity analysis may be performed according to their derived actual strata instead of the randomized strata, i.e. any participants mis-stratified in IVRS will be included in the stratified log-rank test using the strata based on baseline data collected in the eCRF. This analysis will be performed if >10% of participants are mis-stratified in IVRS.

The Cox-model estimate of the log-hazard ratio and its standard error will be used to construct a modelbased estimate of the confidence limits on the HR. The confidence limits are first constructed for the log HR and then exponentiated to provide the corresponding confidence limits on the HR scale. In case of ties in reporting event times, the Efron option in the SAS procedure PHREG will be used.

The log HR estimate obtained from the Cox proportional hazard model is a consistent (asymptotically unbiased) estimate. However, the Cox-model based estimate of the standard error is biased when the proportional HR model assumption does not apply. Thus, if the test for the statistical significance of the coefficient associated with the interaction of survival time and treatment group is nominally significant at the 0.10 level, then the robust sandwich estimate (Li and Wei [1989]; Lachin [2000]) will be employed to provide a consistent estimate of the variance of the log HR estimated from the proportional HR model. The resulting robust confidence limits on the HR will then have the desired coverage probability even though the proportional HR assumption may not apply for the treatment effect.

Vaccine efficacy will be calculated as $VE = 1 - Hazard Ratio \left(\frac{BCG}{Placebo}\right)$

The 95% CI for vaccine efficacy will be derived using the HR CI as follows:

- $VE_{lower limit} = 1 Hazard ratio_{upper limit}$
- VE_{upper limit} = 1 Hazard ratio_{lower limit}

The following information will also be summarized in tables for the mITT efficacy population and repeated for the PP efficacy population:

- Initial QFT conversions by calendar month (mITT efficacy population only).
- Sustained conversion rates with 95% confidence intervals for each treatment group. 95% CIs will be constructed based on the Miettinen and Nurminen method without stratification (Miettinen O, Nurminen [1985]).
- Overall sustained conversion incidence rates along with 95% CIs will be determined based on the total event/censoring time used as denominator. The sequence of sustained conversions will be modelled to follow approximately a Poisson process with constant

intensity θ . The rate parameter θ will be estimated as $\lambda = D/T$, where $T = \sum_{j=1}^{n} t_j$ and D is

the number of participants with a sustained conversion and time t_i (i=1,...n) is the time to sustained conversion if observed, or if not observed, the censored time. Conditional on T, an exact 100*(1- α)% confidence interval for a Poisson variable with parameter θ T and observed value D can be obtained using an exact 100*(1- α)% confidence interval for D/T will be derived as follows:

Lower confidence limit
$$L = \frac{0.5c_{\alpha/2,2D}}{T}$$
 for D>0, 0 otherwise,

Upper confidence limit
$$U = \frac{0.5c_{1-\alpha/2,2D+2}}{T}$$

where $c_{\alpha,k}$ is the α^{th} quantile of the Chi-square distribution with k degrees of freedom.

The following figures will be presented for the mITT efficacy population and repeated for the PP efficacy population:

• Kaplan-Meier plots for time to initial conversion and time to sustained conversion, with tick marks to identify censored observations by treatment group.

Sustained conversion rates and incidence rates will be repeated by site, age, sex, and method of reporting previous BCG vaccine subgroups for the mITT efficacy population only.

Additional listings will be produced, including whether the participant had the event or not (for initial conversion, early QFT reversion, sustained conversion, and end of trial conversion), date of event/censored date, the start date, and the time to event.

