9.4.4. Subgroup Analyses

The consistency of results with respect to the primary and secondary objectives will be examined within various subgroup populations (eg, site, sex, and age group). Details will be provided in the SAP.

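### The SAP undertakes to examine consistency of efficacy across subgroups but pre-specifies only subgroup rates: no subgroup HR or VE with CI, and no interaction estimate

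*SAP*

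**What the plan says.** - **Aim.** Protocol 9.4.4: "The consistency of results with respect to the primary and secondary objectives will be examined within various subgroup populations", with site, sex and age group as examples. It leaves the method open: "Details will be provided in the SAP". SAP 5.2 takes this up: "The consistency of results with respect to the primary and secondary objectives will be examined within the following subgroups using the mITT analysis population". It lists study site/school quintile, sex, age group (10-11, 12-14, over 14) and method of reporting previous BCG.
- **Output.** SAP 9.1, for the mITT population only: "Sustained conversion rates and incidence rates will be repeated by site, age, sex, and method of reporting previous BCG vaccine subgroups". These two outputs are defined just before: conversion rates with 95% CIs, worded as intervals per arm and attributed to Miettinen and Nurminen; and Poisson incidence rates D/T with exact limits.
- **Efficacy measure.** SAP 9.1 defines VE as 1 minus the HR, with limits from the stratified Cox model. This is specified for the overall analysis, and SAP 9.2 adds VE from the interval-censored sensitivity analysis. No section applies either to a subgroup.
- **Secondary objectives.** SAP 9.3 describes the 36- and 48-month analyses and mentions no subgroup output.
- **Two related places.** SAP 7.6 says efficacy analyses will be shown by site/school quintile and refers to other sections for detail, without naming an estimator. The Appendix 7 code for the Miettinen-Nurminen interval uses `riskdiff (CL=mn)`, a between-arm option.

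**The concern.** Consistency of efficacy is a statement about the between-arm effect: is the HR, and so VE, similar across subgroups? The planned table gives a rate per arm within each subgroup. The reader must form the contrast, choose an interval for it and judge heterogeneity without pre-specified guidance. The easy shortcut, checking whether the two arms' intervals overlap, is a poor guide.

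The age strata are where this matters most. Protocol 2.1 names enrolment from age 10 as one of three changes from the previous trial, and SAP 7.2 says that information on attack rate and potential VE at ages 10-11 is limited. A pre-specified VE with its interval would show directly how much or how little the trial learned there. If the method is chosen after unblinding, the choice is open to question.

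**Working it through.** **1. The plan's own figure.** SAP 7.2: "If the true vaccine efficacy is 45%, at least 118 events are required to achieve 90% power or greater". Inputs: HR = 1 - 0.45 = 0.55, one-sided alpha 0.025, power 90%, 1:1 allocation. Schoenfeld: E = 4(1.960 + 1.282)² / (ln 0.55)² = 117.6, so 118; power at 118 events is 90.1%. The figure reproduces, and no number in the plan is disputed.

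**2. What the planned output shows.** Take a subgroup with half the events, 59, split 38 placebo and 21 BCG with equal person-time (an assumed illustration).
- Planned output: exact Poisson limits on the counts of 26.9 to 52.2 and 13.0 to 32.1. They overlap.
- Contrast from the same counts: rate ratio 21/38 = 0.553; SE(log) = √(1/21 + 1/38) = 0.272; VE 45%, 95% CI about 6% to 68%.

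The data for a VE point estimate are in the table, but the estimate, its interval and its comparison with other subgroups are not specified.

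**3. What the coded risk difference would show.** With VE 45% everywhere, the difference is 0.45 times the placebo rate. At the planning attack rates of 8% and 10% it is 3.6 and 4.5 percentage points. SAP 4.1 stratifies randomization because incidence is expected to differ, so risk differences would vary across subgroups even with constant VE.

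**4. Precision after the fix.** The documents give no subgroup event rates. Assume that events follow enrolment, that the sexes split 50:50, and that true VE is 45% throughout. Shares at ages 10-11: about 10% (the cap in SAP 4.1) or 12% (SAP 7.2). SE(log HR) = √(4/E); VE limits = 1 - 0.55·exp(±1.96·SE).

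| Subgroup | Events | SE | 95% CI for VE |
|---|---|---|---|
| All | 118 | 0.184 | 21% to 62% |
| Each sex | 59 | 0.260 | 8% to 67% |
| Age 10-11, 10% share | 11.8 | 0.582 | -72% to 82% |
| Age 10-11, 12% share | 14.2 | 0.531 | -56% to 81% |

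**5. Interaction.** SE of the log ratio of HRs = √(4/E1 + 4/E2). The smallest ratio detectable with 80% power at two-sided 0.05 is exp((1.96 + 0.84)·SE). The last column is the power to detect VE of 60% against 30%, where |ln(0.40/0.70)| = 0.560.

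| Comparison | SE | Detectable ratio of HRs | Power |
|---|---|---|---|
| Sex (59 v 59) | 0.368 | 2.8 | 33% |
| Age 10-11 v older (11.8 v 106.2) | 0.614 | 5.6 | 15% |
| Age 10-11 v older (14.2 v 103.8) | 0.566 | 4.9 | 17% |

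**The case against.** The sponsor has fair answers, and several stand in part.

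- **SAP 7.6 already promises efficacy analyses by site/school quintile.** It does, so the plan is not silent. But it covers one of four subgroups, names no estimator, and the sections it refers to add only the rates.
- **The Appendix 7 code yields a between-arm contrast.** It would, but SAP 9.1 describes the interval as per arm, so text and code disagree. A risk difference also does not measure consistency of VE (step 3).
- **VE can be derived from the incidence rates.** True for the point estimate. A reader might infer that the report could not inform on consistency at all; the documents do not support that. What is missing is a pre-specified interval and a heterogeneity measure.
- **Secondary outputs are left to a separate document (SAP 4.2.2), and 5.2 covers the secondary objectives.** So the silence of 9.3 is a drafting gap and does not show that no output is intended.
- **Sparse sites make Cox estimates unstable.** SAP 7.6 expects low enrolment at some sites or schools. This argues for a pooling rule.
- **The fix would not establish consistency.** Correct: interaction power is 15% to 33% in the examples.

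A reader might also infer that VE outside the Western Cape is at stake. The documents do not support this. Region is not a subgroup in SAP 5.2; SAP 4.1 and protocol 6.3.1 justify the regional cap by consistency with literature data; and geography is not among the three changes listed in protocol 2.1.

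**Conclusion.** The point holds as a mismatch between a stated aim and its specified method. The effect measure on which the trial will be judged is not pre-specified within any subgroup, and neither is a measure of how it varies between them. No primary or secondary conclusion changes, and the sample size is unaffected.

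The benefit is modest. Under the assumptions in step 4, subgroup VE would be moderately informative by sex and very imprecise at ages 10-11. The true event count there could be higher or lower than about 12, since the attack rate in that group is poorly known. This is a low-cost improvement that should be made before unblinding.

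**What to change.** In SAP 9.1 and 9.3:

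1. For each SAP 5.2 subgroup, report HR and VE with 95% CI from the stratified Cox model in a forest plot. Drop the stratification factor that defines the subgroup (age group for the age analysis, sex for the sex analysis).
2. Report a treatment-by-subgroup interaction estimate with its CI. Label all of this output descriptive.
3. Define the site/school-quintile analysis promised in SAP 7.6, and fix before unblinding a rule for pooling sites or quintiles with too few events for a Cox estimate.
4. Reconcile the Miettinen-Nurminen text in 9.1 with the Appendix 7 code: state whether the interval is for each arm's rate or for the between-arm difference, and name a method that fits.
5. State that precision will be low, especially at ages 10-11, and that wide overlapping intervals are not evidence of consistent efficacy.

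The cost is a few more model runs on data already collected and some SAP text. Because the output is descriptive, the step-down testing in SAP 7.8 is untouched.
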